Moisture Management Liner Effectiveness Study

Investigators	[name] Liberating Technologies, Inc. [name] [contact]
	[name] Vivonics, Inc. [name]
Sponsor	U.S. ARMY MEDICAL RESEARCH ACQUISITION ACTIVITY (USAMRAA)
Sponsor Protocol #	E00572.1a
Solutions IRB #	2020/01/01

1. Background and Introduction

The comfort and fit of the residual limb within a prosthetic socket are of primary concern for many amputees. The residual limb is typically covered by non-breathable and non-thermally conductive materials that can create a warm and ultimately moist environment. These layers consist of a prosthetic liner that rolls onto the limb and traps heat and occasional extra prosthetic socks. Studies found increases in socket temperature after the prosthesis was donned (0.8°C) [1] and after 30 minutes of walking (2.5°C) [2]. Temperatures were found to remain elevated long after activity cessation and even a rest period of double the duration of the preceding activity period is insufficient to return the limb to its initial temperature [3]. Peery, et al. [1] suggested that a modest temperature increase of only 2°C may be responsible for reports of thermal discomfort by amputees. Therefore, a small amount of activity can cause the socket temperature to elevate and remain at an uncomfortable level for an extended period of time, which can lead to decreased wear times. In summary, an uncomfortable socket/residual limb interface decreases prosthesis use among amputees who want to remain active in their lives.

To address this, Vivonics, Inc. and Liberating Technologies, Inc. (LTI) have developed a silicone liner approach to wick sweat from the skin and out of the socket through specially designed microchannels and to passively conduct heat from the skin using thermally conductive elastomers. This liner has been developed to work alongside a thermo-electric cooling (TEC)-based module called the Intrasocket Cooling Element (ICE) developed in a parallel project by Vivonics and LTI. The ICE device can be embedded into the prosthesis in order to cool the residual limb. A technology that can provide thermal control while retaining adequate suspension, weight, and other prosthetic characteristics would benefit many prosthesis wearers.

2. Study Rationale

This study will focus on investigating the efficacy of this novel moisture and thermal management (experimental) liner.

The rationale for this study is to determine how well the new technology can regulate the residual limb temperature, reduce the moisture generation, and remove excess moisture in a controlled laboratory environment.

3. Objectives

The primary objective of this study is to measure the effects experimental techniques of moisture and thermal management has on moisture and temperature in the socket. Moisture and thermal management of the residual limb inside the prosthetic socket could result in greater comfort while wearing the prosthesis, and ultimately could result in greater function and better quality of life (QoL).

4. Study Design

A repeated measures study will be conducted to analyze the temperature and moisture generation of the residual limb with and without the experimental liner and active cooling system within a standard prosthetic socket.

Both able-bodied research subjects, and lower limb amputee research subjects who use transfemoral or transtibial prostheses will be recruited for testing. Liners for able-bodies subjects will have the distal end removed to allow for donning. All subjects will visit Liberating Technologies, Inc. to be consented and to complete study testing.

Test conditions include:

- **Control condition.** This would be a non-modified control liner (such as commercially off the shelf (COTS) liners or ones made without any additives) for able-bodied subjects and, for amputees, a check socket (with or without an unmodified control liner, depending on whether the amputee typically wears a liner or not).
- **Experimental liner condition.** This would be a prototype liner designed to reduce and/or remove moisture and heat that builds up on the limb.
- **Active cooling condition.** This would integrate the TEC module (see Figure 1) into the socket for amputees (with the experimental liner or with a control liner), or the TEC module with the experimental or control liner for able-bodied subjects.

Passive cooling and moisture management will be achieved from an experimental liner made of standard silicone used in COTS liner with bio-compatible thermally conductive additives. A standard check socket will be fabricated for each amputee subject if necessary to fit the experimental liner. Additional modifications, such as channels in a liner and socket, may be used to remove moisture such as ones developed under New England IRB (NEIRB) protocol NEIRB # 14-232/HRPO Log A-17885.

Active cooling will be achieved by embedding a TEC assembly into a standard prosthetic socket and liner. The TEC assembly is comprised of a thermoelectric cooling unit (TEC), heat sink, fan and heat spreader and has previously been tested under New England IRB (NEIRB) protocol NEIRB # 120160413/HRPO Log A-17885.2. An experimental socket with the integrated heat spreader will be fabricated for each amputee subject. The amputee subjects will either visit their prosthetist's office

Figure 1. TEC Module embedded into standard prosthetic socket for active cooling condition.

or LTI's in-house prosthetist for measurements and the new socket will be fabricated. The subjects may return for alignment and adjustment on the new socket.

Testing will measure the temperature, humidity, socket suspension and moisture accumulation of the limb when active cooling, moisture/thermal management, and no cooling is applied in order to determine the effectiveness of the proposed technology.

Walking will be used to increase the temperature of the limb in order to measure the system's ability to cool it as well as to determine subject perception of heat and comfort with the experimental liner and active cooling system as compared to the control liners and sockets.

Research participants will have socket temperature and moisture data collected while walking on a treadmill in the different conditions throughout different site visits. The active cooling from the ICE module will be completed with the experimental liner as well as with the control liner. The order of conditions with the experimental and control liners and the active cooling on or off will be randomized for each subject.

5. Study Population

Both able-bodied persons and persons with transfemoral and transtibial limb loss who are able to walk with a prosthesis will be recruited for this study. Able-bodied subjects will be recruited via word of mouth. LTI will enlist the aid of its current in-house prosthetist, [name], CPO and its network of prosthetists including Next Step B&P, Cornell O&P, and several others, to assist in subject recruitment and will be given flyers to hand out to their patients. Additionally, flyers will be distributed online (i.e. LTI's website: LiberatingTech.com/research-studies) and in person by LTI to persons who may be within the target population. If subjects are interested in participating, they can call the number on the flyer and schedule a time to discuss the study with the investigators.

A maximum of 10 able-bodied and 20 lower-limb amputee subjects will be recruited for this study. This is increased from a target 12 subjects to account for any drop-outs, etc.

6. Participant Eligibility

Lower limb amputees will be identified who meet the following inclusion criteria: must be 18-89 years old, be willing and able to complete the tasks outlined, are at least 6 months on a definitive prosthesis, fits within an experimental liner, and can understand English in order to be properly consented and provide their feedback to the study personnel. Subjects can be excluded at the discretion of the investigator for other unforeseen disqualifying criteria (such as specific cognitive issues, etc.).

Subjects in this study will not be discriminated by sex or race.

The risks to pregnant women and fetuses are unknown and therefore pregnant women should not participate in the study and will be screened by self-disclosure.

7. Study Methodology

Visit 1: During the first visit, the subject will be consented and enrolled in the study. Measurements and molds will be taken of the residual limb so an experimental socket can be fabricated. For the purposes of this study, the prosthetic liner is being standardized and all subjects will be provided with a prosthetic liner of the proper size, such as an Iceross Comfort Liner by Ossur or the Superior Performance Liner by ALPS, that has been deemed appropriate by a certified prosthetist

and matches the thickness of the experimental liner. Similarly, if a subject typically uses prosthetic socks, they will be provided with a standardized gel sock instead, such as the Silosheath gel sock by Silipos, of the proper size that has been deemed appropriate by a certified prosthetist.

The experimental liner will be tested on the subject to ensure proper fit and comfort as determined by a certified prosthetist. The subject may be asked to wear the liner without a prosthesis while at home before the second visit to acclimate to the liner(s) as is standard care. During this visit the subject will be asked to completed standard questionnaires regarding their quality of life with their current liner. These will include questionnaires commonly used such as the Dermatology Life Quality Index [4,5], the Residual Limb Health section of the Prostheses Evaluation Questionnaire (PEQ) [6], and the EuroQol-5D.

The experimental socket would be created to fit the subject while wearing the gel sock (if applicable) and appropriate liner using standard clinical socket fabrication techniques. As part of the standard of care when fabricating a new prosthetic socket, the prosthetist first creates a check socket with which to test the fit on the subject before fabricating the definitive socket. Check sockets are structurally sound to walk on and use but may be a littler bulkier and heavier than a definitive socket. Because all testing will be completed in-lab, the check socket will be used for all research activities. LTI will fabricate the prosthetic sockets and install the ICE units in them.

At the same time the prosthetist fabricates the socket, s/he may also create a clear, limb “template” similar to the check socket that matches the limb without accommodating any liner or socks (skin fit). This template allows the location of the sensors on the limb to be marked on the template so that the sensors can be placed in the same location on the limb for each lab test visit.

This visit will take up to 2 hours.

Visit 2: When the experimental socket has been fabricated and instrumented, the subject will return to the lab for a second visit. The subject will be asked to meet with the prosthetist to try on the check socket for fit and alignment with the control and experimental liners.

The subject will then perform in-laboratory testing to determine the effectiveness of an experimental liner to keep the limb cooler and dryer as compared to the control prosthetic liner. The order of conditions (Experimental Liner versus Control Liner, with or without the active cooling ICE unit) will be randomized.

Similar to what was done in a prior protocol under a previous effort (NEIRB # 120160413/HRPO Log A-17885.2), an array of temperature sensors will be attached to the subject’s residual limb before donning the socket and/or liner to give a more complete picture of the overall temperature distribution across the residual limb. Baseline readings will be taken of the residual limb temperature, the body’s core temperature via an oral thermometer, and the ambient temperature.

In addition, we will measure the amount of perspiration produced during each condition. The limb will be dried with a towel, so pre- and post-activity weight of the liner and towel will be measured and the difference in weight is attributed to the sweat produced during that condition as described by Wernke et al. [7]. Testing may also be performed in a thermal chamber that regulates the temperature of the testing area, such as that used by Klute et al. [8], to ensure that the subject will perspire.

In addition, humidity sensors will be attached to the subject's residual limb before donning the socket and/or liner similar to work completed by Cutti et al. [9]. These will allow a more complete picture of the onset of moisture on the residual limb during activity.

In addition, marks will be made with a skin safe marker on the leg where the top of liner rests before the subject begins the testing activity (such as walking on a treadmill). Once the testing activity has ended, the same mark will be made on the leg where the top of the liner rests. The distance between these lines will show any slippage that occurred during the activity which may be due to a lack of suspension.

The subject will be asked to do the following tasks, similar to Klute et al. [3]: (1) an initial seated rest for up to 60 minutes to obtain baseline in-socket temperature data; (2) an activity to increase their body temperature, such as walking on a treadmill [2, 3] for up to 30 minutes; (3) a seated rest for up to 60 minutes; and (4) the liner and perspiration will be collected off the limb (with a towel) and weighed for changes. The second condition will begin once baseline temperatures have been reached and the test procedure repeated in the other condition

Throughout the in-lab test sessions, photos and/or videos may be taken to document such things as the location of the sensors on the limb, the temperature gradients across the limb (with a thermal camera), etc. At the end of each condition, subjective feedback on the comfort and temperature regulation of each condition will be obtained via a questionnaire developed during this effort. The participants would fill out the questionnaire rating parameters such as perceived comfort, intra-socket temperature, potential loss of suspension, etc.

This visit will take up to 4 hours.

This visit can be repeated at the subject's volition, if more data is required or if re-testing is needed.

Visit 3: The same tasks as described in Visit 2 will be completed using the same data collection process. The order of conditions (Experimental Liner versus Control Liner, with or without the active cooling ICE unit) will be randomized. The subject will perform in-laboratory testing to determine the effectiveness the ICE unit to cool and reduce moisture generation of a residual limb with an experimental liner as compared to with a standard control prosthetic liner.

We expect to demonstrate that even if the socket doesn't reduce the temperature during walking, it can cool the socket immediately upon cessation of walking, unlike the standard socket that produces the sustained high temperatures observed by Klute, et al. [3] and Huff, et al. [2]. This benefit is expected to increase with the addition of the experimental thermally conductive liner.

This visit will take up to 4 hours.

This visit can be repeated at the subject's volition, if more data is required or if re-testing is needed.

Once all testing is completed, the research participant will complete a questionnaire to describe their opinions on the comfort, look, and functionality of the experimental liner and ICE unit.

8. Study Conduct

Subjects will be consented and screened for eligibility criteria. If they decide to participate, an experimental liner will be made that fits the size and shape of their limb and an experimental socket to fit the experimental liner will be fabricated using standard prosthetic techniques.

Subjects may withdraw at any time by simply telling the investigators they wish to stop their participation.

If a subject withdraws from the study, the data that were collected from them can still be used, and the withdrawn subjects may be replaced with a new subject. Deviations from the protocol that increase risks for subjects will be reported to Solutions IRB and HRPO for approval prior to being implemented.

The consent process and all testing will be completed at the Liberating Technologies, Inc. research facility located in Holliston, MA. Approved study staff from Vivonics, Inc. may also be present during testing visits to provide technical support or monitor testing activities. During these visits approved study staff from Vivonics, Inc. may be in contact with the subjects.

Subjects will be compensated \$40 per hour for the 3 visits for the in-lab testing and prosthetist visits for an estimated total of \$400 (10 hours) per subject. Travel will also be reimbursed per mile at the current IRS federal rate.

9. Study Treatment

This is not a treatment study. The purpose of the study is to evaluate the effectiveness of a moisture removal and thermally conductive liner.

10. Evaluation of Adverse Events

Based on past testing and data collection, no adverse events are expected. Adverse events could include: discomfort or dermatological reaction to experimental liner materials or sensors in the socket, tripping while walking on the treadmill, overheating or overcooling due to controller, sensor, or battery malfunction of the ICE unit. These risks have been mitigated by using biocompatible materials and/or hypoallergenic tape with the sensors, using a spotter during walking tasks for in-lab testing, and standard thermal and electrical management techniques including thermal battery management, voltage/current limiting, and monitoring temperature during testing.

All unanticipated problems involving risk to subjects or others, serious adverse events related to participation in the study and subject deaths related to participation in the study will be promptly reported to the Solutions IRB and HRPO. A written description of the adverse event will be stored in the study file maintained by the Principal Investigator. Also, the protocol will be reviewed in light of the adverse event to determine if modifications need to be made to prevent the event from occurring again. Major modifications to the research protocol and any modifications that could potentially increase risk to human subjects must be submitted to the Solutions IRB and HRPO for approval prior to implementation.

11. Ethical Considerations

There is no direct benefit to the user. Participating in this study may potentially advance the scientific community's understanding on the ability of reducing intra-socket moisture generation and cooling intra-socket temperatures to improve comfort and quality of life for lower limb amputees.

The protocol, consent form, and recruitment flyer will require IRB review and approval. The principal investigator will be in continuous communication with the IRBs and HRPO and will forward information to the co-investigators. Subjects' participation is voluntary, and they may withdraw from participation in the study at any time by simply telling any one of the investigators that they wish to stop. The investigators may choose to terminate a subject's participation if he or she experiences discomfort or injury. In addition, participants will be given any new information which is discovered during the course of the study which may influence participants' willingness to continue the study. If they desire to do so,

subjects' will also have the option to discuss any concerns regarding the study activities or the investigators with an impartial staff member of the site IRB, whose duty it is to hear and review such concerns and provide advice or take any other appropriate actions.

The investigators will ensure the anonymity of all participants in this study. After completing the consenting process, subjects will be assigned a random identification number. The number will be used on all test data associated with the subject. No personal identifiers will be associated with the data collected from the subjects during the various tests. The PI will have a master document linking the subject name with ID number, and it will be stored on a password protected computer, with only the PI and approved study staff having access to the master list. All collected test data will be kept at Liberating Technologies, Inc. and stored in a secure manner depending on the media: either a password protected computer with access limited to the co-investigators, or in a locked filing cabinet in the investigator's office. A copy of the test data will also be retained by the PI in the program folder, also stored in a secured manner. Deidentified test data may also be stored at Vivonics, Inc. using the random identification numbers assigned to subjects.

12. Study Monitoring and Oversight

The oversight of the study falls on the PI and co-investigators. They will be responsible for ensuring the study follows the approved protocol and for reporting any deviations or adverse events that occur during the study to Solutions IRB and HRPO. De-identified data, photos, and videos will be kept indefinitely to show in scientific presentations and publications. Photos will not contain any identifying information about the subject. The photographs will not include the subject's face or any identifying marks such as tattoos. If identifying photographs happen to be received from a subject, they will be de-identified by either cropping or blurring using photo-editing software.

Additionally, representatives of the United States Army Medical Research Acquisition Activity (USAMRAA) are eligible to review research records as a function of their responsibility to protect subjects in research.

13. Investigational Product Management

The experimental liners tested in this study are modified to increase the thermal conductivity and remove moisture from the limb to regulate intra-socket temperature and reduce moisture accumulation. The ICE technology tested in this study is a cooling device for the residual limb that is an add-on system to a standard prosthetic socket. Additionally, commercially-available temperature and humidity sensors may also be used in the instrumented sockets.

EXPERIMENTAL LINER

The experimental liner is a product of mixing thermally conductive additive to a base silicone material. The base material is a medical grade room temperature curing silicone rubber (RTV-2) from Wacker Chemie AG with characteristics of biocompatibility, low surface tension, thermal and chemical stability. This silicone can be sterilized easily for single as well as repeated use. The nature of the silicone is hydrophobic which prevents microbial growth. Additives such as boron nitride, carbon and graphene nanoparticles are added to enhance the thermal conductivity of the liner. These nanomaterials are skin safe and are currently being used in other skin contacting applications such as cosmetics and wearable electronics [10, 11, 12, 13].

The experimental liner will be manufactured and packaged at a manufacturing facility that makes COTS liners using the standard procedures.

INTRASOCKET COOLING ELEMENT

The ICE active cooling module is comprised of a combination of: 1) an inner Heat Spreader (isothermal) layer designed to maintain approximately constant temperature along a section of the inner wall of the socket and 2) a Heat Extractor

providing a heat channeling pathway utilizing: a) a Thermo-Electric Cooling (TEC) module, b) a heat radiator (heat sink) structure and c) an air circulating system (fan) to discharge the heat to the surrounding air.

The heat spreader functions to collect heat from around the circumference of the limb and then route it to a much smaller and more focal point where it is expelled from the socket by the heat extractor. Additionally, the system has been developed to work in conjunction with commercially-available prosthetic liners where the heat spreader is in contact with the liner, not the skin, and pulls the excess heat through the liner to extract it.

The active heat pumping mechanism that is used in these devices is a thermoelectric cooler (TEC). TECs are semiconductor devices that use electrical current to pump heat from one side of the device to the other based on the Peltier effect. As an active system, a TEC can chill the heat source (residual limb) to a temperature lower than its surroundings. In the ICE system, the TEC is used to pump heat from the heat spreader to a heat sink acting as a radiator. The TEC raises the heat sink to a temperature above ambient. A fan then facilitates removal of heat from the heat sink. The TEC heat pumping action is particularly useful in high ambient temperature situations where the heat sink and fan alone would not be able to sufficiently cool the hot side of the heat spreader.

The ICE unit is powered by a standard, commercially-available 2 cell Li-ion rechargeable battery pack, such as the Tenergy 18650 7.2V 3500mAh battery, and is housed in a case to protect against damage. This battery has protection circuitry, including over-charge, over-discharge and short-circuit protection, and is being charged with the recommended charger externally, off the subjects. Control of the device is based on a push button where the user engages the button when he/she feels that cooling is necessary and turns off the system when he/she no longer needs cooling. When the device is on, the system will regulate cooling to the limb based on feedback from multiple sensors in the device, including the hot and cold side temperatures of the TEC. As long as the cold side of the TEC is above the minimum threshold, the TEC will be powered to reduce the limb temperature while taking into account battery life. As the cold side temperature approaches the threshold temperature, the voltage to the TEC will be reduced to maintain a TEC cold side temperature above the threshold. Prior studies have shown that applying cooling at a temperature of 22°C (72°F) is the lowest temperature that is uniformly well-tolerated [5]. Because we will have a prosthetic liner between the ICE cooling element and the skin, we will use a cold side threshold temperature that takes into account the thermal properties of the standardized liner to ensure a residual limb temperature of no less than 22°C. Our testing has shown that the cold side threshold can be as low as 11.5°C (53°F) and still maintain a skin temperature of greater than 22°C. Therefore, based on this data, we will use 11.5°C as our minimum cold side temperature threshold; however, we may iterate the control algorithm and adjust the threshold as needed as more data is collected that can inform the algorithm.

SOCKETS

The prosthetic interface used in this study will be fabricated by a Board-Certified Prosthetist, following conventional standardized methods. The “ICE System” is to be incorporated into the socket design with manufacturing techniques similar to those used to integrate commercially-available prosthetic components and add-ons, such as suction valves, shuttle locks, elevated vacuum systems (e.g. Ohio Willow Wood ONE system), etc and used in a prior approved protocol (NEIRB # 120160413/ HRPO Log A-17885.2). The inclusion of the “ICE System” will be such that the structural integrity and functionality of the socket will not be compromised. The socket characteristics will be similar to the subject’s usual socket, monitoring and maintaining acceptable mobility and comfort throughout the testing procedure.

CONTROL LINERS

The control liners tested in this study will either be commercial-off-the-shelf (COTS) products that are approved for the general population or made with only the base silicone of the experimental liners. We have standardized the control liner used for this study in order to eliminate confounding factors of liner material and thickness.

PROSTHETIC SOCKS

The prosthetic socks in this study will be commercial-off-the-shelf (COTS) products that have been identified to work well with the ICE system, for example, the Silosheath gel sock by Silipose.

TEMPERATURE SENSORS

Commercially available temperature sensors, such as thermistors, thermocouples and iButtons, may be used to monitor the temperature of the ICE device as well as the temperature of the residual limb inside the prosthetic socket. The thermistors and thermocouples have been used in the approved protocols for the previous and current studies (NEIRB # 120160413/ HRPO Log A-17885.2). The iButton has been used in O&P clinical practice and research studies to monitor temperatures within O&P devices [15].

HUMIDITY SENSORS

Commercially available humidity sensors, such Sensirion SHT21S, may be used to monitor the humidity of the residual limb inside the prosthetic socket. This humidity sensor has been used in another research study on prosthetic sockets following a similar protocol by Cutti et al. [9].

14. Data Analysis

The data collected in the laboratory will include limb temperature, ambient temperature, limb humidity, ambient humidity, and moisture generation on the limb. Standard outcomes measures will include: Dermatology Life Quality Index, Modified Dermatology Life Quality Index, the Residual Limb Health section of the Prostheses Evaluation Questionnaire (PEQ), and the EuroQol-5D. Custom questionnaires that were developed to assess the experimental liner and ICE system will also be used.

The primary outcome of this study will assess the effect of the experimental liners on the temperature of the residual limb; however secondary measures include moisture generation and humidity on the residual limb as well as satisfaction with the prosthesis using the above measures. Measures during the experimental liner conditions will be compared to the control conditions both with and without the ICE system being active.

15. References

- [1] J. T. Peery, W. R. Ledoux, and G. K. Klute, "Residual-limb skin temperature in transtibial sockets," *The Journal of Rehabilitation Research and Development*, vol. 42, no. 2, pp. 147–154, 2005.
- [2] E. A. Huff, W. R. Ledoux, J. S. Berge, and G. K. Klute, "Measuring Residual Limb Skin Temperatures at the Skin-Prostheses Interface," *JPO Journal of Prosthetics and Orthotics*, vol. 20, no. 4, pp. 170–173, Oct. 2008.
- [3] G. K. Klute, E. Huff, and W. R. Ledoux, "Does Activity Affect Residual Limb Skin Temperatures?," *Clinical Orthopaedics and Related Research®*, vol. 472, no. 10, pp. 3062–3067, Jun. 2014.
- [4] A. Finlay and G. Khan, "Dermatology Life Quality Index (DLQI)-a simple practical measure for routine clinical use," *Clinical and Experimental Dermatology*, vol. 19, no. 3, pp. 210–216, 1994.
- [5] H. Meulenbelt, J. Geertzen, M. Jonkman, and P. Dijkstra, "Skin Problems of the Stump in Lower-limb Amputees: 2. Influence on Functioning in Daily Life," *Acta Dermato Venereologica*, vol. 91, no. 2, pp. 178–182, 2011.
- [6] D. A. Boone and K. L. Coleman, "Use of the Prostheses Evaluation Questionnaire (PEQ)," *JPO Journal of Prosthetics and Orthotics*, vol. 18, no. Proceedings, 2006.

- [7] M. M. Wernke, R. M. Schroeder, C. T. Kelley, J. A. Denune, and J. M. Colvin, "SmartTemp Prosthetic Liner Significantly Reduces Residual Limb Temperature and Perspiration," *Journal of Prosthetics and Orthotics*, vol. 27, no. 4, pp. 134–139, Oct. 2015.

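### Section 4 makes the amputee control liner depend on habit, while the rest of the protocol assumes a control liner for everyone; followed literally, it changes the ICE-off comparison for habitual non-liner users

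*Protocol*

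**What the plan says.** **Section 4, Control condition.** For amputees the control is "a check socket (with or without an unmodified control liner, depending on whether the amputee typically wears a liner or not". Whether a liner is worn depends on the subject's habit.

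**Section 4, Active cooling condition.** The cooling module is integrated "into the socket for amputees (with the experimental liner or with a control liner". No option without a liner is given.

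**Section 4, randomization.** "The order of conditions with the experimental and control liners and the active cooling on or off will be randomized for each subject". This is a two-by-two layout of liner type and ICE state, with no cell without a liner. Section 7 repeats it for Visits 2 and 3.

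**Section 6.** Amputees qualify if, among other things, they "are at least 6 months on a definitive prosthesis, fits within an experimental liner". Habitual liner use is not required.

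**Section 7, Visit 1.** "the prosthetic liner is being standardized and all subjects will be provided with a prosthetic liner of the proper size", matched in thickness to the experimental liner. "The experimental socket would be created to fit the subject while wearing the gel sock (if applicable) and appropriate liner".

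**Section 7, Visit 2.** Subjects "try on the check socket for fit and alignment with the control and experimental liners". For perspiration, "pre- and post-activity weight of the liner and towel will be measured". Slippage is read from skin marks at the liner's upper edge.

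**Section 13, Control Liners.** The control liner is said to have been standardized so that liner material and thickness do not confound the comparison.

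**Section 14.** The primary outcome is the experimental liner's effect on residual limb temperature, compared with control in both ICE states.

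**Appendix B.** The individual session forms for Visits 2 and 3 offer only Control or Experimental as the liner worn.

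**The concern.** The control condition is defined in two incompatible ways, and the difference bears on the primary comparison. Section 1 says a liner traps heat, so a limb in a bare check socket cannot be assumed to have the same temperature as a limb in a control liner. An amputee tested under the Section 4 parenthesis would contribute an ICE-off contrast that mixes the effect of the liner's design with the effect of wearing any liner at all.

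The same subject's ICE-on contrast would still be liner versus liner, so the two contrasts would no longer estimate the same thing. Within the control condition, ICE on versus off would also compare control liner plus ICE with no liner and no ICE. Any statement about whether the liner works better with ICE than without it would be affected for that subject.

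**Working it through.** The protocol gives no figure on this point to reproduce. The check is a comparison of texts, followed by an illustration on assumed inputs.

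**Step 1. The cells for an amputee who does not normally wear a liner**

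| | ICE off | ICE on |
|---|---|---|
| Sections 7 and 13 and the randomization text | experimental liner vs control liner | experimental liner vs control liner |
| Section 4, Control condition | experimental liner vs no liner | experimental liner vs control liner |

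The two rows differ only in the ICE-off cell: 1 of the 2 liner contrasts. Able-bodied subjects and habitual liner users have the same cells under both readings.

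**Step 2. Can the case arise?** Yes. Section 6 does not screen out non-liner users, and the parenthesis itself anticipates them. No sentence ranks Section 4 against Section 7.

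**Step 3. What the altered contrast measures.** Let E, C and N be limb temperature with the experimental liner, the control liner and no liner, all with ICE off.

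- Intended contrast: d1 = E − C
- Contrast under Section 4: d0 = E − N = (E − C) + (C − N)
- Difference: d0 − d1 = C − N

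If a liner traps heat, as Section 1 says, C − N is positive and d0 is shifted against the experimental liner. The protocol gives no value for C − N.

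**Step 4. Size if such sessions are pooled.** Inputs: n = 20, the maximum number of amputees (Section 5); k = 1, 3 or 5 affected (assumed).

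- Shift in the mean ICE-off contrast = (k/n)(d0 − d1)
- k = 1: 1/20 = 0.05 °C per 1 °C of d0 − d1
- k = 3: 3/20 = 0.15 °C per 1 °C
- k = 5: 5/20 = 0.25 °C per 1 °C
- Shift in the ICE-on minus ICE-off difference = (k/n)(d1 − d0): the same amounts with the opposite sign

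If d0 − d1 is assumed to lie between 0.5 and 2.0 °C, the ICE-off shift runs from 0.05 × 0.5 = 0.025 °C to 0.25 × 2.0 = 0.5 °C. If d0 = d1, it is zero. Section 5 also mentions a target of 12 subjects without saying which group; one affected subject in 12 would be 1/12 = 8.3%, against 5% of 20.

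**Step 5. Size if such sessions are set aside.** There is no shift, only loss of ICE-off pairs. With equal variance per subject, the standard error is multiplied by √(20/(20 − k)):

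- k = 1: 19 pairs, √(20/19) = 1.026, about 2.6% larger
- k = 3: 17 pairs, √(20/17) = 1.085, about 8.5% larger
- k = 5: 15 pairs, √(20/15) = 1.155, about 15.5% larger

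**Step 6. Secondary measures.** Without a liner, the liner part of the sweat weight and the reference edge for slippage do not exist. A socket shaped over a liner would also fit differently without one.

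**The case against.** The strongest reply is that Section 7 is the working procedure and is consistent throughout: everyone receives a liner, the socket is built over it, and the forms have no place for a no-liner session. Staff following it would never run one, so the parenthesis is a leftover. This is plausible and limits the likely harm. It does not remove the conflict, because Section 4 is where the control condition is formally defined.

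A second reply is that no sentence strictly requires the liner to be worn. Section 7 says it is provided, the Section 13 statement about a liner between cooling element and skin concerns ICE use, and Section 14 speaks of control conditions rather than control liners. On the letter this is right. Still, the randomized conditions, socket fit, measurements and forms all presuppose a worn control liner.

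Third, the parenthesis may be a deliberate comparison with the subject's usual set-up. That reading does not fit the stated reason for standardizing the control liner, nor the absence of any socket, randomized cell or form for a no-liner session.

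Three further points stand. Towel weighing still captures some limb sweat without a liner. A visit may be repeated, so a lost contrast could be recovered. The numbers affected are assumed, and the standard-error figures presuppose a paired analysis in amputees alone, which the protocol does not specify.

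**Conclusion.** The concern holds. The contradiction is certain on the text; its effect on results is conditional and may be zero. Bias in the primary contrast needs three things: a habitual non-liner user enrols, staff apply the Section 4 definition, and the session is pooled with the others. If the session is set aside, only precision is lost.

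Per affected amputee, one of two liner contrasts is lost unless the visit is repeated. Across the amputee group the shift is the affected share multiplied by an unknown temperature difference, and neither factor is given in the protocol. The point should be fixed: it concerns the definition of the comparator for the primary outcome, and a later analysis cannot supply a control-liner session that was never run.

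**What to change.** Reconcile Section 4 with Sections 7 and 13. Replace the parenthesis so that the amputee control reads: *a check socket with the standardized control liner described in Section 7*, and state that this applies with ICE off and with ICE on.

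Add that any session nevertheless run without a liner is kept out of the primary liner-versus-liner contrast and reported separately. This second rule may sit in the statistical analysis plan, which was not available for this review.

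The cost is protocol wording only, since Section 7 already supplies every subject with a liner. The one real loss is that the control no longer reflects the everyday set-up of amputees who do not use a liner. If the sponsor wants that comparison as well, it needs its own named condition.
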